Appendix B. BOR Calculation Algorithm

Confirmed BOR by Investigator

At each time point, BOR will be derived based upon the evaluated time points up to and including the current assessment. The following rules will apply to BOR:

- CR is better than PR is better than SD is better than PD is better than NE
- For a BOR of SD, a duration of ≥ since the cycle 1 is required
- For a BOR of CR, PR or PD, confirmation is required in a consecutive assessment ≥ after the initially observed assessment of CR, PR or PD except the following cases
 - An unlimited number of intermittent assessments of NE or CR can occur between the initial response and the confirmation of CR. For example, BL, CR, NE, NE, NE, CR the CR at post-baseline 1 is confirmed at post-baseline 5. SD is not allowed between CR and subsequent confirmation CR.
 - An unlimited number of intermittent assessments of NE, SD, PR or CR < can occur between the initial response and the confirmation of PR. For example, BL, PR, SD, SD, SD, PR – the PR at post-baseline 1 is confirmed by post-baseline 5.
 - An unlimited number of intermittent assessments of NE can occur between the initial PD and the confirmation. (No reference though)
 - PD doesn't need confirmation if PD is the last evaluable assessment PD and determines BOR or PD time of PFS.

Table 8 provides the BOR determination per modified RECIST 1.1 for trials where confirmation for response and progressive disease are required. A BOR determined by Table 8 is considered a Confirmed_BOR. Table 9 outlines the steps to derive Confirmed_BOR (step 1) given investigator's time point assessments.

Interim BOR by Investigator

At interim futility analyses, due to lack of sufficient follow-up time for confirmation san, study team may choose to report both confirmed responders and unconfirmed responders (subjects had an initial PR or CR and still has potential for future confirmative scans). Interim BOR is defined to include unconfirmed responders in addition to those who achieve Confirmed BOR. Table 9 step 2 is the step to derive these unconfirmed responders.

Confirmed and Interim BOR by Central Review

Date: 27 Sep 2024 Page 47 of 51

Confirmed and Interim BOR by Central Review will be derived from Time point response by Central. The steps are same as derivation for Confirmed and Interim BOR by Investigator (Table 8 and Table 9)

Protocol Number: 20200439

Date: 27 Sep 2024 Page 48 of 51

Product: AMG 757, AMG 404

Table 8. BOR per Modified RECIST 1.1

		1	1			
Criterion	Timepoint T1 Response	T1 ≥ (X- 1)* after C1 ?	Timepoint T2 Response	T2 ≥ (X- 1)* after C1 ?	T2 ≥ after T1?	BOR_temp
C1	CR	Yes	CR	-	Yes	CR
C2			CR	-	No	SD
C3			PR, SD	-	-	Query data*
C4			PD	-	-	SD
C5			NE, No further	evaluations		SD
C6		No	CR	-	Yes	CR
C7			CR	Yes	No	SD
C8			CR	No	No	NE
C9			PR, SD	-	-	Query data*
C10			PD	-	-	NE**
C11			NE, No further	evaluations		NE
C12	PR	Yes	CR, PR	-	Yes	PR
C13			CR, PR	-	No	SD
C14			SD	-	-	SD
C15			PD	-	-	SD
C16			NE, No further	evaluations		SD
C17		No	CR, PR	-	Yes	PR
C18			CR, PR	Yes	No	SD
C19			CR, PR	No	No	NE
C20			SD	Yes	-	SD
C21			SD	No		NE
C22			PD	-	-	NE**
C23			NE, No further	evaluations		NE
C24	SD	Yes	CR, PR, SD, F	PD, NE, no mo	re evaluation	SD
C25		No	CR, PR, SD	Yes	-	SD
C26			CR, PR, SD	No	-	NE
C27			PD	-	-	NE**
C28			NE, No further	evaluations		NE
C29	PD	-	CR, PR, SD	Yes		SD
C30			CR, PR, SD	No		NE
C31			PD		Yes	PD
C32			PD		No	NE**
C33			NE, No further	evaluations		NE**
C34	NE	-	NE, No further evaluations			NE
C35		-	CR, PR, SD	Yes	-	SD
C36		-	CR, PR, SD	No	-	NE
C37		-	PD	-	-	NE**

Date: 27 Sep 2024 Page 49 of 51

CR = complete response, PR = partial response, SD = stable disease, PD = progressive disease, and NE = not evaluable.

X is the scan schedule of every X weeks per protocol. X=8

*If a CR is truly met at first time point, then any disease seen at a subsequent time point, even disease meeting PR criteria relative to baseline, makes the disease PD at that point (since disease must have reappeared after CR). Best response would depend on whether minimum duration for SD was met. However, sometimes 'CR' may be claimed when subsequent scans suggest small lesions were likely still present and in fact the patient had PR, not CR at the first time point. Under these circumstances, the original CR should be changed to PR and the best response is PR.

** For rows C10, C22, C27, C32, C37, if timepoint T2 response of PD is the last evaluable assessment, then BOR_temp is PD, otherwise the BOR_temp is NE. For row C33, if timepoint T1 response of PD is the last evaluable assessment, then BOR_temp is PD, otherwise the BOR_temp is NE.

Table 9. BOR Derivation Step

Derive Confirmed BOR at each visit:

- i) At Visit 1: Using the Visit 1 scan result and refer to **Table 8** to derive *Confirmed BOR*.
- ii) At Visit 2 onward:
 - (a) If current visit is CR, PR or PD: Find last scan that is at least before current visit. Derive BOR_temp as below:

Last scan	Current	BOR_temp
CR	CR	CR
PR	CR	PR
PR	PR	PR
PD	PD	PD

- (b) If none of above fits, find last scan reference **Table 8** to derive *BOR_temp*.
- iii) Current visit Confirmed BOR = best of (BOR_temp, last visit confirmed BOR). Use rule CR > PR > SD > PD > NE

Step 2. Derive Interim BOR at last visit prior to DCO

For subjects who discontinue tumor assessment (i.e. had confirmed PD, next therapy, or end of study):

[figure not shown]
For subjects with potential for more assessment (i.e. no confirmed PD, next therapy, or end of study), unconfirmed PR/CR can be considered responders.

Date: 27 Sep 2024 Page 50 of 51

	•	If any scan is CR and haven't get the
Assign Interim BOR = Confirmed		opportunity to receive next scan, then Interim
BOR		BOR = CR.
	•	If any scan is PR and haven't get the
		opportunity to receive next scan, then Interim

BOR = PR.

Date: 27 Sep 2024 Page 51 of 51

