For parameters/assessments not scheduled to be performed (or scheduled but not performed) on the same day as the earliest date of first administration of tarlatamab or AMG 404 the baseline value is the value from the screening period measured closest to the day earliest date of first administration of tarlatamab or AMG 404. In the event that multiple assessments are done on the same day as the earliest date of first administration of tarlatamab or AMG 404 and there is no time associated with the assessments, the value associated with the last clinically planned event before the earliest date of first administration of tarlatamab or AMG 404 will be used as the baseline value.

Baseline ECG

Baseline ECG is the Cycle 1 pre-dose assessment. If Cycle 1 pre-dose assessment is missing, the last non-missing assessment(s) taken prior to the first administration of tarlatamab or AMG 404 treatment will be used as the baseline ECG.

Date: 27 Sep 2024 Page 22 of 51

Best Overall Response (BOR)

Best overall response (BOR) for a subject is the best observed post baseline disease response per modified response evaluation criteria in solid tumors (modified RECIST 1.1). Overall response assessments occurring after the start of the first subsequent anticancer therapy will not be included.

BOR is defined as the best response in the following order: CR, PR, SD, PD, or NE, where CR, PR and PD require confirmation by a repeat, consecutive scan at least 4 weeks after the first documentation of response. A best overall response of SD requires an on-study imaging of SD or better no earlier than days after cycle 1 otherwise the best overall response will be not evaluable (NE).

Please refer the Appendix B for more details.

Body Mass Index (BMI)

Body Mass Index should be calculated using the following formula

BMI
$$(kg/m^2)$$
 = weight (kg) / [height $(cm)/100$]²

Body Surface Area (BSA)

The Body Surface Area should be calculated using the following formula

BSA=
$$0.007184 \times weight(kg)^{0.425} \times height(cm)^{0.725}$$

Change from Baseline

Change from Baseline is the arithmetic difference between post-dose assessments and Baseline.

Change (absolute) from Baseline = (Post-baseline Value – Baseline Value)

C_{max}

Maximum observed serum concentration of tarlatamab.

C_{min}

Minimum observed serum concentration of tarlatamab.

Disease control rate (DCR)

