Long term follow-up will be conducted every 3 months (±2 weeks) up to 1 year from the first dose of tarlatamab for all subjects who have not withdrawn consent by clinic visit, telephone, or chart review to assess for survival and/or the commencement of subsequent cancer therapy only.

For subjects who discontinued treatment for any reason other than confirmed progressive disease, every effort should be made to perform radiographic imaging (computed tomography [CT]/MRI) of the chest, abdomen, pelvis, and all other known sites of disease every 3 months until documentation of confirmed disease progression per modified RECIST 1.1, clinical progression, start of new anticancer therapy, or up to 12 months after the first dose of tarlatamab, whichever occurs first.

Modified Toxicity Probability Interval (mTPI)

Date: 27 Sep 2024 Page 26 of 51

The modified toxicity probability interval for target dose-limiting toxicity (DLT) probability of 30% is defined as equivalence toxicity of interval as (25%, 33%) and probability of overdosing of 95% with Beta (1,1) as the prior distribution.

Objective response (OR)

Objective Response is defined as a best overall response of either Complete Response (CR) or Partial Response (PR) per modified RECIST 1.1. Radiographic response

(Complete Response, Partial Response) requires confirmation by a repeat, consecutive scan at least 4 weeks after the first documentation of response.

Objective Response Rate (ORR)

ORR is defined as the incidence of a BOR of a confirmed CR or PR while on study as defined by modified RECIST 1.1. All subjects that do not meet the criteria for objective response by the analysis cut-off date will be considered as non-responders.

Objective Response Rate (ORR) based on Unconfirmed Response

ORR based on unconfirmed response is defined as the incidence of a BOR of CR or PR which do not require confirmation while on study as defined by modified RECIST 1.1. Only unconfirmed response awaiting confirmatory scan is considered in the ORR based on unconfirmed response.

Overall Survival (OS)

OS (in Months) is defined as the interval from the earlier date of first dose of tarlatamab or AMG 404 to the event of death due to any cause. Subjects still alive will be censored at the date last known to be alive. If the date last known to be alive is after the date that triggers the analysis (ie, the data cutoff date), the subject will be censored at the analysis trigger date.

Percent change from Baseline

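### SAP Appendix B classifies a partial response interrupted by stable disease in two ways: confirmed under the PR bullet, unconfirmed under the Table 9 derivation

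*SAP*

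**What the plan says.** **The PR bullet.** Appendix B requires CR, PR and PD to be confirmed at a consecutive assessment and then lists exceptions. The PR exception begins "An unlimited number of intermittent assessments of NE, SD, PR or CR" and lets these fall between the first response and its confirmation. Its example is baseline, PR, SD, SD, SD, PR, of which it says "the PR at post-baseline 1 is confirmed by post-baseline 5". The CR bullet, by contrast, rules out SD between a CR and its confirmation.

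**The derivation.** Appendix B also says "A BOR determined by Table 8 is considered a Confirmed_BOR" and "Table 9 outlines the steps to derive Confirmed_BOR". For a current CR, PR or PD, Table 9 step ii(a) reads "Find last scan that is at least before current visit" (the interval is blacked out). It lists four pairs: CR-CR, PR-CR, PR-PR and PD-PD. Step ii(b) begins "If none of above fits, find last scan reference" and sends the pair to Table 8. Step iii keeps the better of this result and the previous visit's confirmed BOR.

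**The definitions.** Under Best Overall Response, SAP Section 5 says "CR, PR and PD require confirmation by a repeat, consecutive scan at least 4 weeks after the first documentation of response" and refers to Appendix B for details. Its Objective Response definition says that radiographic response "requires confirmation by a repeat, consecutive scan at least 4 weeks after the first documentation of response". Protocol 11.9 asks for a repeat, consecutive assessment at least 4 weeks later for both CR and PR, and mentions no exception for SD. SAP Section 10 declares no changes from the protocol-specified analyses.

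**The concern.** The bullet states a rule and gives an example. The table is the procedure that a programmer would code. Run on the bullet's own example, the table gives a different answer. Two programmers who each follow the SAP faithfully could report different ORRs, and different sets of subjects would enter duration of response and time to response, both of which are limited to responders. Appendix B applies the same steps to central review, so the problem is not confined to investigator assessment. In addition, a reader who relies on Section 10 would not learn that a PR interrupted by SD can count as confirmed, which protocol 11.9 does not provide for.

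**Working it through.** **Inputs.** Scans every 8 weeks (Table 8 note, X = 8). Minimum time for SD is X - 1 = 7 weeks (Table 8 column heading). The confirmation interval is blacked out in Table 9 and is assumed to be 4 weeks, from SAP Section 5; on an 8-week grid any interval up to 56 days gives the same result.

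**The worked example, PR, SD, SD, SD, PR at weeks 8, 16, 24, 32 and 40**

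- Bullet: confirmed PR.
- Table 9, visit 1: PR with no second scan, at least 7 weeks from start. Row C16 gives SD.
- Visits 2 to 4: the current scan is SD, so step ii(a) does not apply. Step ii(b) gives SD (row C14, then C24).
- Visit 5: the current scan is PR and the last scan at least 4 weeks earlier is the SD at week 32. SD-PR is not among the four pairs, so step ii(b) applies and row C24 gives SD. Step iii takes the best of SD and SD.
- Table 9 result: SD, a non-responder.

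With 6-week spacing, and with 4-week spacing after week 8, the final result is also SD. The control sequence PR, PR gives PR.

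**Short sequences under three readings**

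| Scans | Bullets | Table 9, literal last scan | Table 9, NE skipped |
|---|---|---|---|
| PR, SD, PR | PR | SD | SD |
| PR, SD, SD, SD, PR | PR | SD | SD |
| PR, NE, PR | PR | SD | PR |
| CR, NE, NE, NE, CR | CR | SD | CR |
| PR, PR | PR | PR | PR |

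The SD rows disagree under either reading of the table. The NE rows disagree only if the last scan is taken to include not-evaluable ones.

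**All PR/SD/NE sequences on the 8-week grid.** Under the bullets a subject responds with two or more PRs, so the count for n scans is 3^n - 2^n - n x 2^(n-1):

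- n = 3: 27 - 8 - 12 = 7
- n = 4: 81 - 16 - 32 = 33
- n = 5: 243 - 32 - 80 = 131

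Table 9 needs two adjacent PRs, literally or after NE scans are dropped.

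| Scans | Sequences | Bullets | NE skipped | Literal | SD conflict | NE wording |
|---|---|---|---|---|---|---|
| 3 | 27 | 7 | 6 | 5 | 7 - 6 = 1 | 6 - 5 = 1 |
| 4 | 81 | 33 | 26 | 21 | 33 - 26 = 7 | 26 - 21 = 5 |
| 5 | 243 | 131 | 99 | 79 | 131 - 99 = 32 | 99 - 79 = 20 |

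Disease control is the same under all readings in all 27 + 81 + 243 = 351 sequences, because SD counts as disease control. These are counts of patterns, not patient frequencies.

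**Size if one subject is affected.** The protocol's own precision statement (Section 9.2) reproduces: 2/10 = 20% has exact interval 2.5-55.6% (stated 3-56%), and 4/20 = 20% has 5.7-43.7% (stated 6-44%). One more responder gives 3/10 = 30% (6.7-65.2%) or 5/20 = 25% (8.7-49.1%).

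**The case against.** **The bullet is a stated exception.** A reader might infer that the PR bullet breaks the SAP's own consecutive rule. The documents do not support that: Appendix B introduces the bullet as an exception to the rule, and the BOR definition in Section 5 refers to Appendix B. The Objective Response definition repeats the consecutive wording, but it defines response through BOR. What stands is that Table 9 does not carry out the exception, and that protocol 11.9 has no such exception while Section 10 declares no change.

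**Table 8 is not at fault.** Table 8 does not say that T1 and T2 must be adjacent. Pairing visit 1 with visit 5 directly gives row C12, which is PR. The conflict comes from Table 9's pairing with the last scan. To reach PR, Table 9 would have to search back past SD, and it does not say so.

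**Not-evaluable gaps.** A reader might infer that Appendix B contradicts itself on NE scans as well, because literal Table 9 returns SD for the CR, NE, NE, NE, CR example. That is too strong. Appendix B bases BOR on evaluated time points, and its bullets allow NE gaps, so skipping NE is the natural reading and removes the difference. The NE rows for T1 in Table 8 (C34-C37) leave some room for the literal reading, so the wording should be clarified.

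**Redaction.** Text in the PR bullet after the permitted states is blacked out, so the exact limits of the SD allowance cannot be seen. The worked example is complete and legible, however, and it is enough to show the conflict.

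**Limited effect.** ORR is secondary and descriptive, no hypothesis is tested, the intervals are wide, and no affected subject is shown. This limits the weight of the point but does not decide which classification applies.

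**Conclusion.** The point holds in a narrow form. For a PR followed by SD and then PR, the Appendix B bullet gives a responder and Table 9 gives a non-responder. The result does not depend on how NE scans are handled or on which of the tested scan spacings is used. It rests on reading Table 9's last scan as the most recent qualifying scan and on a 4-week confirmation interval.

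ORR, and entry into duration of response and time to response, are affected; disease control is not, in the PR/SD/NE sequences tested. One affected subject would move ORR by 5 percentage points at n = 20 or 10 points at n = 10. How many subjects have this pattern cannot be known from the documents. A reader might infer from the 32 of 243 five-scan patterns that about 13% of subjects would be reclassified (32/243 = 0.132). That does not follow, because the patterns are not equally likely in patients.

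The allowance for SD may be deliberate, since the CR bullet forbids SD and the PR bullet permits it. In that case Table 9 is wrong and the departure from protocol 11.9 is undeclared. If it is not deliberate, the bullet is wrong. The text needs to change either way.

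**What to change.** Choose one branch before database lock, without reference to the responder data. This matters because the study is open-label, enrollment ended in January 2023 (protocol 4.1) and the SAP is dated 27 September 2024.

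**Branch A, follows protocol 11.9.** Remove SD from the PR bullet and replace its example. In Table 9 step ii(a), use the last evaluable (non-NE) scan at least the minimum interval before the current visit. For the CR-CR, PR-CR and PR-PR pairs only, add that no SD or PD scan may fall in between. Leave PD-PD out of this clause: with PD at days 14, 28 and 42 and a 28-day interval, the clause would let the PD at day 28 block the day 14 to day 42 confirmation.

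**Branch B, keeps the bullet.** Leave SD in the PR bullet. For the PR-PR and PR-CR pairs, let step ii(a) search back past SD and NE scans to an earlier PR at least the minimum interval before, with no PD in between. Keep SD disallowed for CR-CR. Do not add the no-SD clause to the PR pairs, since that would recreate the conflict. Declare the departure from protocol 11.9 in Section 10.

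**Both branches.** State in Table 9 that NE scans are skipped, and note this in Section 10. If any subject is classified differently under the other branch, report that ORR as a sensitivity count.

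**Cost.** A few sentences in Appendix B and Section 10 and a small reprogramming of Table 9, with no change to data collection. ORR may be slightly lower under Branch A.

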Appendix C. PFS Calculation and Censoring Rule

Table 10 defines PFS censoring rule per modified RECIST 1.1 PD from radiographic scans.

Table 10. PFS Censoring Rule

Situation up to DCO/EOS	Date of Event or Censor	Outcome
No evaluable post-baseline tumor assessments, no death recorded	Date of Randomization date (or first dose date of IP in non- randomized trials)	Censor
PD	Date of first detection of PD	Event
No PD, but death recorded	Date of death	Event
Start of new anti-cancer therapy prior to any PD or death	Date of last evaluable tumor assessment before or on start of new anti-cancer therapy	Censor
	Date of last evaluable tumor assessment	Censor
more missed tumor assessment (18	Date of last evaluable tumor assessment prior to missing assessment(s) ^a	Censor

Note: PD's does not require confirmation if based on RECIST 1.1.

DCO = Data Cutoff; EOS = End of Study; PD = Progressive disease ^a This supersedes the previous rules that result in PFS event at date of PD or death.

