8.1.4 Long-term Follow-up

Long term follow-up will be conducted every 3 months (\pm 2 weeks) up to 1 year from the first dose of tarlatamab for all subjects who have not withdrawn consent by clinic visit, telephone, or chart review to assess for survival and/or the commencement of subsequent cancer therapy only.

For subjects who discontinued treatment for any reason other than confirmed progressive disease, every effort should be made to perform radiographic imaging (computed tomography [CT]/MRI) of the chest, abdomen, pelvis, and all other known sites of disease every 3 months until documentation of confirmed disease progression per modified RECIST 1.1, clinical progression, start of new anticancer therapy, or up to 12 months after the first dose of tarlatamab, whichever occurs first.

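### The single missed-scan limit in SAP Table 10 fits 8-weekly scans but not the 3-monthly off-treatment scans, so one missed scan there can turn a PD, or a death more than 18 weeks after the last scan, into a censoring

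*SAP*

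**What the plan says.** **The rule.** The last row of SAP Appendix C, Table 10, deals with events after missed scans. Its label is incomplete in the text available; what can be read is "more missed tumor assessment (18". The count before it and the unit after it cannot be read. The date assigned is the "Date of last evaluable tumor assessment prior to missing assessment(s" and the outcome is a censoring. Footnote a gives the row priority: "This supersedes the previous rules that result in PFS event at date of PD or death". Table 10 shows no other missed-scan limit.

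**The on-treatment schedule.** The footnote to Table 8 in SAP Appendix B states "X is the scan schedule of every X weeks per protocol. X=8". SAP 6.5 requires 9 weeks since first dose for the Interim Efficacy Analysis Set.

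**The off-treatment schedule.** For subjects who stop treatment for a reason other than confirmed PD, Protocol 8.1.4 asks sites to try to image the chest, abdomen, pelvis and "all other known sites of disease every 3 months until documentation of confirmed disease progression". Imaging also stops at clinical progression, at new anticancer therapy, "or up to 12 months after the first dose of tarlatamab, whichever occurs first". SAP Section 5 (Long Term Follow-Up) repeats this and sets the survival contacts: "Long term follow-up will be conducted every 3 months (±2 weeks) up to 1 year from the first dose of tarlatamab". Protocol 8.4.7 separately asks for the vital status of all subjects and gives no end date.

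**Reach.** SAP Section 5 applies the Appendix C censoring to DOR and DoDC as well as PFS. SAP 9.5.2 plans no sensitivity analysis for PFS or DOR.

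**The concern.** A limit in weeks tolerates a fixed number of missed scans only while the scan interval stays fixed. Here the interval lengthens from 8 weeks to 3 months when a subject stops treatment without confirmed PD. The same 18 weeks that forgives one missed scan on treatment would forgive none afterwards.

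Whether a PD counts as an event would then depend on treatment status as well as on disease. The subjects concerned stopped for toxicity or other non-PD reasons, so the censoring may be informative. Missed scans are also easier to foresee in this phase, because the protocol asks for best effort rather than requiring the scan.

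A second gap follows from the same row. Once imaging has stopped as planned, time since the last scan keeps growing although nothing has been missed. A late death could then be treated as following missed assessments.

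**Working it through.** **Inputs.** Scan interval on treatment: 8 weeks (SAP Appendix B). Limit: 18, read as weeks (SAP Table 10). Scan interval off treatment: 3 months (Protocol 8.1.4). Long-term follow-up window: ±2 weeks, taken here to apply to scans too (an assumption). Visit window from cycle 3: ±3 days (Protocol 1.3). End of off-treatment imaging: month 12 at the latest.

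1. **Reproducing the 18.** Two 8-week intervals with one week's allowance each: 2 x (8 + 1) = 18. The 9 weeks in SAP 6.5 equals one such interval, which supports the weeks reading.

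2. **On treatment.** One missed scan leaves 2 x 8 = 16 weeks (up to 16.9 with both windows), so the event is kept. Two leave 3 x 8 = 24 weeks (at least 23.1), so it is censored. The limit separates one miss from two.

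3. **Off treatment.** 3 months = 3 x 365.25 / 12 / 7 = 13.0 weeks. For two scans that both fall in the 3-monthly phase:
   - No miss: 13 ± 4 = 9 to 17 weeks. Event kept.
   - One miss: 26 ± 4 = 22 to 30 weeks, above 18 throughout. A PD at that scan is censored 22 to 30 weeks earlier.
   - A death after one missed scan remains an event up to week 18 after the last scan and is censored only beyond that.

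4. **If a count governs.** Suppose the row requires two missed scans and the count decides. One missed 3-monthly scan then does not trigger it, although the 18 beside it is exceeded. Two programmers could reasonably code this differently.

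5. **After imaging stops as planned.** 18 weeks = 18 x 7 / 30.4375 = 4.1 months. With a last scan at month 12, only deaths after about month 16.1 are at risk. The same can happen earlier: imaging stops at clinical progression, which Protocol Appendix 9 classes apart from radiographic PD. Such a subject who takes no new therapy and dies more than 18 weeks after the last scan could be censored.

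6. **A scaled limit.** Two 3-month intervals plus 2 to 4 weeks: 2 x 13 + 2 = 28, or 2 x 13 + 4 = 30. Two missed scans leave 3 x 13 ± 4 = 35 to 43 weeks, so 30 still separates one miss from two. 28 covers the nominal 26 but not the last two weeks of the window.

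7. **Illustrative simulation of off-treatment subjects.** Every input is an assumption: treatment stops at week 12, median time to PD is 13 or 26 weeks, median PD to death is 20 weeks, and deaths are followed to month 12. Share of observed events turned into censorings:

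| Chance of missing each scan | 18-week limit | 28-week limit |
|---|---|---|
| 0% | 0% | 0% |
| 10% | 9.4 to 10.2% | 0.5 to 0.7% |
| 20% | 18.2 to 19.5% | 2.3 to 2.5% |

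Under 8-weekly scans (median 26 weeks) the 18-week limit converts 1.5% and 5.7% at 10% and 20% missed.

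8. **How many subjects.** Withdrawals for treatment-related events in the cited first-in-human study were 3.7% in Part A1 overall and 15% in cohort 10, with none in cohort 8. No adverse event led to discontinuation in Parts A2 and C. Taking about 40 subjects (inferred from the average sample sizes in Protocol Table 9-3), 0% to 15% is 0 to 6 subjects. At 10 to 20% of events converted, 6 x 0.10 = 0.6 and 6 x 0.20 = 1.2. Stops for other non-PD reasons would add to this.

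9. **Direction.** Take ten subjects with events at months 1 to 10 and censor the month-10 event at month 4. At month 4, S = 0.60 either way; afterwards 5 subjects remain at risk instead of 6. S(5) = 0.60 x 4/5 = 0.48 against 0.50, S(6) = 0.60 x 3/5 = 0.36 against 0.40, and S(9) = 0 against 0.10. The curve falls. If instead the month-8 event is censored at month 2, S(7) = 0.80 x 2/7 = 0.23 against 0.30, but S(8) = 0.23 against 0.20. The curve is lower inside the gap and higher after it.

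**The case against.** The strongest objection is that the row cannot be read in full. Its count, its unit and anything after the 18 are not legible, and the complete wording may already settle the matter. That stands as a caution, so the point is conditional: on the weeks reading the limit is too short off treatment, and on the count reading the two criteria disagree. Either way the legible table has only one limit for two schedules.

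It is also fair that censoring after a long gap is a deliberate and common choice. After 26 weeks without a scan the true PD date is unknown, and dating PD at detection may be late. That supports keeping a missed-scan rule, but not letting its tolerance change with treatment status.

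A reader might infer more than the documents support:

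- *That any death after one missed scan is lost.* A death within 18 weeks of the last scan stays an event.
- *That month 12 opens a large hole.* Routine survival contacts end then too, and without scans there is no radiographic PD to convert. Only deaths after about month 16, learned through vital-status checks, are exposed, and the plan does not establish how many would be captured. Subjects still on treatment keep their scheduled scans.
- *That PFS and DOR are necessarily lengthened.* The example in the working shows otherwise.
- *That 1 to 6 of 40 subjects are affected.* The lower end leaves out the groups with no withdrawals, and the figure counts subjects exposed to the rule. To be affected, a subject must also miss a scan, or outlive planned imaging, and then have a late event before new therapy.

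**Conclusion.** The point holds as a mismatch between one censoring limit and two imaging schedules. On the weeks reading, a single missed off-treatment scan is enough to censor a PD at the next scan, at every point of the 22-to-30-week range, and to censor a death more than 18 weeks after the last scan. On the count reading, the count and the 18 contradict each other off treatment. Deaths after imaging stopped as planned form a narrower, secondary gap.

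The likely effect is none to a few subjects, in either direction, on PFS, DOR and DoDC. PFS and DOR are secondary endpoints, all three are descriptive, and no hypothesis is tested; OS, ORR and the safety endpoints are untouched. The conclusion rests on reading 18 as weeks, on applying the ±2-week window to scans, and on an inferred sample of about 40. It is a cheap improvement worth making, and it does not undermine the trial's main conclusions.

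**What to change.** In SAP Table 10:

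- Define the limit as two scheduled intervals plus window under the imaging schedule in force: 18 weeks on 8-weekly scans, and about 28 to 30 weeks on 3-monthly scans (30 covers the full window).
- State whether the count of missed scans or the elapsed weeks governs.
- Apply the row only to scans that were scheduled, so that a death after planned imaging ended is an event on its date.
- Add a sensitivity analysis for PFS, DOR and DoDC that counts every recorded PD and death as an event, ignoring this row.

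The cost is one reworded row and one extra run, with no new data. The downside is that a PD found after one missed 3-monthly scan is dated at detection, which may be late; reporting both versions shows how much that matters.
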